6 INVESTIGATIONAL PLAN

6.1 Overall study design

This is a prospective, open-label 2 year PAS evaluating radiographic appearance of Radiesse implantation in the dorsum of the hands in 20 subjects (40 hands). All subjects will be new subjects who did not participate in the pre-market Radiesse hand treatment study (Merz #P110607). Subjects will be consented at 1 investigational site in the United States.

Multiple assessments will be performed at study visits. Some of the main assessments include:

- X-rays – X-rays will be taken at a licensed radiographic imaging center and transmitted to the imaging core lab to be assessed by two blinded, licensed radiologists
- MHGS (**Figure 1**) – a single blinded site evaluator will grade the hands using the MHGS

- MHQ – subjects will self-report assessment of the effect(s) of Radiesse injection on hand function using the MHQ
- GAIS (**Table 1**) – subjects will rate the aesthetically pleasing aspect of the Radiesse hand treatment using the GAIS
- AE Subject Diary – subjects use this to collect any AEs for 30 days post injection
- Photographs – at baseline and exit from the study, and during the study to document a serious or medically concerning adverse event in the hands.

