Week 1/Initial treatment visit: 7 ± 6 days from enrollment, all subjects will return for a follow-up visit after completing the corresponding X-ray visit to the designated imaging center. This visit can be scheduled on the same day as the X-ray visit. Females of childbearing age will complete a urine pregnancy test. The subject's hands will be assessed on the MHGS by a live, masked evaluator. Subjects will complete the MHQ [REDACTED] [REDACTED]. At this time, subjects will receive a Radiesse treatment. A take-home 30-day diary will be given to the subject. A physician will assess the subject's hands for AEs. Photographs of the hands will be taken only in the event of a serious or medically concerning AE. Subjects will be scheduled for the Month 1 X-ray and follow-up visits.

Follow-Up Evaluations

72 hours after Week 1/initial treatment: Subjects will be scheduled for a phone visit 72 hours after treatment to assess for AEs. Subjects will be reminded to continue daily entries into their 30-day diary.

Month 1 X-rays: 30 ± 5 days from enrollment, all subjects will have x-rays taken of their hands at a designated, local, licensed imaging center. This visit must be completed prior to the Month 1 follow-up visit at the investigational site.

Month 1: 30 ± 5 days from initial treatment, all subjects will return for a follow-up visit after completing the corresponding X-ray visit to the designated imaging center. Changes in concomitant medications will be recorded by the study staff. The subject's hands will be assessed on the MHGS by a live, masked evaluator. Subject self-assessment of aesthetic improvement will be performed using the GAIS. Subjects will complete the MHQ [REDACTED].

[REDACTED] A physician will assess the subject's hands for AEs. The take-home 30-day diary will be reviewed for completion and

collected. A physician will assess the subject's hands for AEs. Photographs of the hands will be taken only in the event of a serious or medically concerning AE.

Month 6 X-rays: 180 ± 10 days from enrollment, all subjects will have X-rays taken of their hands at a designated, local, licensed imaging center. This visit must be completed prior to the Month 6 follow-up visit at the investigational site.

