Month 6: 180 ± 10 days from enrollment, all subjects will return for a follow-up visit. Changes in concomitant medications will be recorded by the study staff. The subject's hands will be assessed on the MHGS by a live, masked evaluator. Subject self-assessment of aesthetic improvement will be performed using the GAIS. Subjects will complete the MHQ.

A physician will assess the subject's hands for AEs. A urine pregnancy test will be completed for female subjects of child bearing potential. A Radiesse retreatment will be performed on both hands if agreed upon by treating investigator and subject. A take-home 30-day diary will be given to the subject if a retreatment is received. Photographs of the hands will be taken only in the event of a serious or medically concerning AE.

72 hours after Month 6 retreatment: Only subjects receiving a retreatment at the Month 6 visit will be scheduled for a phone visit 72 hours after treatment to assess for adverse events. Subjects will be reminded to continue daily entries into their 30-day diary.

Month 7: $210 \text{ days} \pm 5$ days from enrollment, only subjects who received a retreatment at Month 6 will return for a follow-up visit. Changes in concomitant medications will be recorded by the study staff. The subject's hands will be assessed on the MHGS by a live, masked evaluator. Subject self-assessment of aesthetic improvement will be performed using the GAIS. Subjects will complete the MHQ.

A physician will assess the subject's hands for AEs. The take-home 30-day diary will be reviewed for completion and collected. Photographs of the hands will be taken only in the event of a serious or medically concerning AE.

Month 12 X-rays: 360 ± 10 days from enrollment, only subjects whose hand bones were not visible in the Month 6 X-rays will have X-rays taken of their hands at a designated, local, licensed imaging center. This visit must be completed prior to the Month 12 follow-up visit at the investigational site.

Month 12: 360 ± 10 days from enrollment, all subjects will return for a follow-up visit. Changes in concomitant medications will be recorded by the study staff. The subject's hands will be assessed on the MHGS by a live, masked evaluator. Subject self-assessment of aesthetic improvement will be performed using the GAIS. Subjects will complete the MHQ.

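### Follow-up after retreatment is timed from enrollment, not from the injection, so the 30-day AE diary can be collected 15 to 45 days after a retreatment, against 25 to 35 days after the first injection

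*Protocol*

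**What the plan says.** Protocol 6.1 gives the diary's purpose: "subjects use this to collect any AEs for 30 days post injection". SAP section 2 repeats it.

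For the first injection, Protocol 9.2 times the Month 1 visit from treatment: "30 ± 5 days from initial treatment, all subjects will return for a follow-up visit". The diary is collected at that visit.

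For retreatments, Protocol 9.2 counts both visits from enrollment. The injection is given at the Month 6, 12 or 18 visit: "Month 6: 180 ± 10 days from enrollment, all subjects will return for a follow-up visit", and at that visit "A Radiesse retreatment will be performed on both hands if agreed upon by treating investigator and subject". Month 12 has the same form ("Month 12: 360 ± 10 days from enrollment, all subjects will return for a follow-up visit"), as does Month 18 at Day 540 ± 10. A new diary is handed out then.

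The diary comes back at Month 7, 13 or 19. Month 7 is set at Day 210 ± 5, counted in "days from enrollment, only subjects who received a retreatment at Month 6 will return for a follow-up visit". Months 13 and 19 are set at Days 390 and 570, ± 5, also from enrollment. The instruction at each is: "The take-home 30-day diary will be reviewed for completion and collected".

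Protocol 6.1.1 describes these visits as one-month follow-ups after each repeat treatment. Neither document says what happens to a diary reviewed before its 30 days are complete.

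**The concern.** A retreatment and its follow-up each move within their own window around a fixed study day. Nothing in the windows ties the second date to the first. A late retreatment followed by an early follow-up shortens the diary period, and a site can do this without a protocol deviation.

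The safety of multiple retreatments is a stated objective (Protocol 5.1; SAP section 5). The AE summaries are to include duration, severity and recurrence (Protocol 12.4.2; SAP 6.3). Milder events, and the stop dates of events still running, are where a daily diary adds most. If it is taken back early, what happens in the missing days is recorded only if the subject calls or remembers it at the next scheduled visit, some four to six months later. The loss runs one way: a 30-day diary collected on day 45 still covers 30 days, while one collected on day 15 covers half.

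The same windows set the timing of the one-month-after-retreatment MHGS and GAIS secondary endpoints (Protocol 5.2 and 12.3.2; SAP 6.4).

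**Working it through.** **Inputs** (Protocol 9.2, days from enrollment unless stated):

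| Injection | Injection window | Collection window |
|---|---|---|
| First | treatment day | 25 to 35 days after treatment (Month 1) |
| Month 6 | 170 to 190 | 205 to 215 (Month 7) |
| Month 12 | 350 to 370 | 385 to 395 (Month 13) |
| Month 18 | 530 to 550 | 565 to 575 (Month 19) |

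**The plan's own figure.** The nominal gaps are 210 − 180 = 390 − 360 = 570 − 540 = 30 days. The 30-day diary fits the centers of the windows.

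**Range allowed.** Shortest gap = earliest collection − latest injection; longest gap = latest collection − earliest injection.
- Months 6/7: 205 − 190 = 15; 215 − 170 = 45.
- Months 12/13: 385 − 370 = 15; 395 − 350 = 45.
- Months 18/19: 565 − 550 = 15; 575 − 530 = 45.

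Up to 30 − 15 = 15 diary days can be lost after a retreatment, against 30 − 25 = 5 after the first injection.

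**When 30 days cannot be reached.** The latest compliant Month 7 date is Day 215. For a retreatment on Day 186 the longest gap is 215 − 186 = 29 days; for Day 190 it is 215 − 190 = 25. So on Days 186 to 190 (5 of 21 permitted dates) no compliant visit completes the diary. The same holds for Days 366 to 370 (395 − 366 = 29) and Days 546 to 550 (575 − 546 = 29).

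**What careful scheduling can achieve.** For a retreatment on Day 170, Day 205 gives 35 days; for Day 190, Day 215 gives 25. Every date in between also has a compliant Month 7 date 25 to 35 days later.

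**How often, if dates fell evenly and independently** (an assumption; the documents give no distribution). There are 21 × 11 = 231 date pairs for each retreatment.
- Under 30 days: 110 (110/231 = 47.6%).
- Exactly 30 days: 11 (4.8%). Over 30 days: 110.
- Under 25 days: 55 (23.8%). Over 35 days: also 55.
- Mean diary days lost: 660/231 = 2.9.
- First injection, collection spread evenly over days 25 to 35: (5 + 4 + 3 + 2 + 1)/11 = 15/11 = 1.4.

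If sites schedule to one month, the loss after retreatment falls to at most 5 days.

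**Table 2.** In the supplied text its windows appear as plus only (+10, +5). Read that way, the gap after a retreatment is 210 − 190 = 20 to 215 − 180 = 35 days. The one-sided signs may be lost characters, so I do not treat them as an error. The contrast with the first injection rests on the 9.2 text.

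**The case against.** A reader might infer that AE capture after retreatment is routinely cut short and biased downward relative to the first injection. The documents do not support that.

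- The nominal gap is 30 days, and 121 of 231 permitted date pairs (52%) give 30 days or more. The 15-day case needs the latest injection with the earliest follow-up.
- Protocol 6.1.1 states a one-month follow-up after each retreatment. A site that follows it can always achieve 25 to 35 days, the range already accepted after the first injection. The 48% and 24% figures ignore that intent.
- Only the diary is affected. All AEs are recorded from consent to the last visit (Protocol 10), there is a 72-hour call after each retreatment, a physician assesses the hands at each follow-up visit, and subjects are told to call about significant hand discomfort or difficulty with activities.
- No comparison of AE incidence by injection number is planned, and the documents give no AE onset times, so the size of any bias cannot be derived. The primary X-ray endpoint is untouched.
- Protocol 8.2.2 describes the diary as recording events up to the next visit, and the diary form (Appendix B) is not in the supplied text. Its return instructions may already cover an unfinished diary.

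All of this limits the point. What remains is that the one-month intent appears in the design description while the operative windows permit 15 to 45 days, and that on late retreatment dates those windows rule out a full 30 days. The fallback routes are also less sensitive than a daily diary: the unscheduled-visit route is framed around significant discomfort or difficulty.

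**Conclusion.** The point holds as a loose timing rule. Under Protocol 9.2 the diary can be collected 15 to 45 days after any of the three retreatments, against 25 to 35 days after the first injection. Diary-based AE capture after retreatment can be truncated and is not uniform across injections. The MHGS and GAIS assessments meant for one month after retreatment can fall anywhere in the same 15 to 45 days.

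The worst case is 15 of 30 diary days lost. The expected loss is modest: about 2.9 days against 1.4 if dates spread evenly, a difference of about 1.5 days, and less if the site schedules to one month. The range follows from the stated windows alone; the averages rest on the even-spread assumption. Whether any AEs would be missed, and how many, is unknown. The case for change is that the correction is nearly free and serves a stated safety objective in a study of only 20 subjects.

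**What to change.** In Protocol 9.2 and Table 2, time Months 7, 13 and 19 as 30 ± 5 days from the actual retreatment date, as Month 1 already is from the initial treatment. Collection then falls 25 to 35 days after every injection, and the MHGS and GAIS follow-ups take the same timing. In days from enrollment, Month 7 could then run from 170 + 25 = 195 to 190 + 35 = 225, well clear of Month 12 (Day 350 at the earliest).

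Add one sentence: if the diary is reviewed before its 30 days are complete, the subject keeps it and returns it when complete. This removes the remaining shortfall of up to 5 days, including at Month 1. A window that opens only on day 30 would do the same but is optional. The SAP section 2 visit description should be checked for consistency.

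The change adds no visits, procedures or X-rays and leaves the retreatment dates alone. It costs some scheduling flexibility and an occasional diary that is returned without in-person review.

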7.4 Removal of subjects from treatment or assessment

7.4.1 Discontinuation of subjects

The subject may volunteer to discontinue or withdraw from the study at any time without any penalty or loss of benefits to which the subject is otherwise entitled. Date and discontinuation circumstances should be recorded.

Subjects must be discontinued from the study by the investigator at any time for any of the following reasons:

- Withdrawal of informed consent.
- Pregnancy.
- Any AE for which treatment continuation would constitute an unacceptably high risk for the subject.

Before discontinuation, every effort should be made to ensure that the subject returns for a final study visit. In the case of loss to follow-up subjects, every effort should be made to contact subjects lost to follow-up, and all such efforts should be documented in the subject file.

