9.2 Visit schedule

Screening and Enrollment

Enrollment will be limited to 20 subjects for the study. The Sponsor will oversee enrollment and be in direct communication with the investigational site to make all efforts not to exceed the enrollment target of 20 subjects, and to ensure that Groups A and B (described in Section 7) are fully enrolled. Presenting subjects may be pre-screened to the selection criteria identified in Sections 7.2 and 7.3. If it is determined that a presenting subject meets these selection criteria, the subject will be given an Informed Consent Form to review and sign.

There will be 3 visits during the screening and enrollment period: 2 at the investigational site, and 1 at the local X-ray imaging center. The X-ray visit may be performed on the same day as the consent or injection.

Upon the subject's provision of informed consent to participate in the study, the subject will be enrolled in the study and assigned a study ID number. The number will contain 3 parts – trial identification code (XR = X-Ray), site identification number, and subject enrollment order number. For example, the third subject enrolled will receive study ID number XR-1-03. The masked evaluator will assess hands on the MHGS to meet hand rating requirements for inclusion. Enrolled subjects will be assigned to Group A or B based on baseline MHGS ratings until both groups are fully enrolled. Study information including demographics and concomitant medications will be recorded, and photographs will be taken of each hand. The subject will then be scheduled for hand X-rays to be taken prior to Radiesse hand treatment.

Within 72 hours after enrollment: Subjects will have X-rays taken of their hands at a designated, local, licensed imaging center.

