Month 19: $570 \text{ days} \pm 5 \text{ days}$ from enrollment, only subjects who received a retreatment at Month 18 will return for a follow-up visit. Changes in concomitant medications will be recorded by the study staff. The subject's hands will be assessed on the MHGS by a live, masked evaluator. Subject self-assessment of aesthetic improvement will be performed using the GAIS. Subjects will complete the MHQ.

A physician will assess the subject's hands for AEs. The take-home 30-day diary will be reviewed for completion and collected. Photographs of the hands will be taken only in the event of a serious or medically concerning AE.

Month 24 X-rays: $720 \text{ days} \pm 30 \text{ days}$ from enrollment, only subjects receiving a total of 4 treatments (initial, 6-, 12, and 18-months) will have X-rays taken of their hands at a

designated, local, licensed imaging center. This visit must be completed prior to the Month 24 follow-up visit at the investigational site.

Month 24: 720 ± 30 days from enrollment, all subjects will return for the final follow-up visit. Changes in concomitant medications will be recorded by the study staff. The subject's hands will be assessed on the MHGS by a live, masked evaluator. Subject self-assessment of aesthetic improvement will be performed using the GAIS. Subjects will complete the MHQ [REDACTED]. A urine pregnancy test will be completed for female subjects of child bearing potential. A physician will assess the subject's hands for AEs. Photographs of the hands will be taken. The subject's study participation will end at this visit.

Unscheduled Visits: Subjects will be instructed to call the investigational site if they experience significant hand discomfort or difficulty performing activities at any point during the 24 month period. At the discretion of the treating investigator, a subject will be requested to appear for an unscheduled study visit for follow-up and potential intervention for an AE of concern. For an unscheduled visit, the subject will be assessed for AEs, concomitant medication update will be obtained, the subject will complete an MHQ, and photographs of the hands will be taken.

Table 2. Schedule of Events.

Assessment	Screen -ing/ Enrollment	X-ray Wk 1	Wk 1†	Mo 1	X-ray Mo 6	Mo 6	Mo 7**	X-ray‡ Mo 12	Mo 12	Mo 13**	Mo 18	Mo 19**	X-ray* Mo 24	Mo 24

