Visit Window (Day)	-7 to 0	Day 3 +- 3	Day 7 +0-7	Day 30 +5	Day 180 +10	Day 180 +10	Day 210 +5	Day 360 +10	Day 360 +10	Day 390 +5	Day 540 +10	Day 570 +5	Day 720 +30	Day 720 +30
Inclusion/ Exclusion	X													
Informed Consent	X													
Demographics	X													
Concomitant Medications	X			X		X	X		X	X	X	X		X
Merz Hand Grading Scale – Masked Evaluator	X			X		X	X		X	X	X	X		X
Michigan Hand Outcome Questionnaire			X	X		X	X		X	X	X	X		X

Subject GAIS			X		X	X		X	X	X	X		X	
Urine Pregnancy Test	Xα		Xα		Xα			Xα		Xα				Xα
X-rays of Hands		X		X††	X††			X‡					X*	
Hand Treatment			X			X ^v			X ^v		X ^v			
72-hour follow-up phone call			X			X**			X**		X**			
Adverse Events – Subject Diary		X	X	X		X**	X**		X**	X**	X**	X**		
Adverse Events – Treating MD		X	X	X		X	X		X	X	X	X		X
Hand Photographs	X		X‡‡	X‡‡		X‡‡	X‡‡		X‡‡	X‡‡	X‡‡	X‡‡		X

† To be scheduled after Week 1 X-ray, and can be on the same day after X-rays are taken

†† Corresponding X-ray imaging center visit must be completed prior to investigational site visit

* To be scheduled only for subjects receiving 4 treatments (enrollment, Months 6, 12, and 18)

** Only if repeat treatment received

‡ To be scheduled only if bones of at least 1 hand are not visible on Month 6 X-rays

‡‡ Only to document a serious or medically concerning adverse event

v Only if treatment is indicated as agreed upon by investigator and subject

α Prior to X-ray or Radiesse treatment

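### At Months 6, 12 and 24 the visit text puts the X-ray before the urine pregnancy test, although Table 2 requires the test first

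*Protocol*

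**What the plan says.** In protocol Table 2 (Schedule of Events), footnote α is attached to the marks in the urine pregnancy test row and reads "Prior to X-ray or Radiesse treatment".

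Section 9.2 (Visit schedule) sets the order of the X-ray and site visits:

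- **Month 6 X-ray** (all subjects): "This visit must be completed prior to the Month 6 follow-up visit at the investigational site".
- **Month 12 X-ray** (only if bones were obscured at Month 6): "This visit must be completed prior to the Month 12 follow-up visit at the investigational site".
- **Month 24 X-ray** (only after four treatments): "This visit must be completed prior to the Month 24 follow-up visit at the investigational site".

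The paragraphs for the Month 6, 12 and 24 site visits each contain the sentence "A urine pregnancy test will be completed for female subjects of child bearing potential". None of the X-ray paragraphs mentions a test. Table 2 footnote ††, which marks the Month 1 and Month 6 X-rays, gives the same X-ray-first order: "Corresponding X-ray imaging center visit must be completed prior to investigational site visit".

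For the baseline X-ray, section 9.2 says "Within 72 hours after enrollment: Subjects will have X-rays taken of their hands at a designated, local, licensed imaging center" and names no test before it. Table 2 does show one at Screening.

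Section 7.4.1 includes pregnancy in the list that begins "Subjects must be discontinued from the study by the investigator at any time for any of the following reasons". The SAP repeats the X-ray schedule but does not deal with pregnancy testing.

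**The concern.** A pregnancy test tied to an X-ray is useful only if its result is known before the exposure. Table 2 states that intention, but a site working from the section 9.2 visit descriptions would take the film first and test afterwards. A pregnancy present at Month 6, 12 or 24 would then be found only after the hands had been X-rayed.

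The protocol treats both matters as important. Pregnancy is an exclusion criterion and a reason for mandatory discontinuation. Section 4.3 lists the risks of ionizing radiation, and section 12.1 justifies the small sample partly by the wish to limit exposure. Women of child bearing potential may enrol if they use effective contraception, so the safeguard applies to a group the protocol admits.

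This concerns subject safety and internal consistency. It has no bearing on the obscuration endpoint or on any analysis.

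**Working it through.** The plan gives no figure to reproduce. The check compares the order of procedures, then works out the timing that the visit windows allow.

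**Order of test, X-ray and treatment under section 9.2, with Table 2 for Screening**

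| Time point | Who is X-rayed | Test before the X-ray? | Test before treatment? |
|---|---|---|---|
| Baseline / Week 1 | all | yes, at Screening (Table 2 only) | yes, at Week 1 |
| Month 1 | all | none scheduled | no treatment |
| Month 6 | all | no, X-ray comes first | yes, if retreated |
| Month 12 | conditional | no, X-ray comes first | yes, if retreated |
| Month 18 | no X-ray | not applicable | yes, if retreated |
| Month 24 | conditional | no, X-ray comes first | no treatment |

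The X-ray part of the rule therefore fails at Months 6, 12 and 24, which is 3 of the 5 X-ray time points. Testing before treatment is listed at all four treatment visits.

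**Windows in section 9.2, in days from enrollment**

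- Week 1: 7 ± 6, so days 1 to 13.
- Month 6 X-ray and site visit: 180 ± 10, so days 170 to 190.
- Month 12 X-ray and site visit: 360 ± 10, so days 350 to 370.
- Month 18: 540 ± 10, so days 530 to 550.
- Month 24 X-ray and site visit: 720 ± 30, so days 690 to 750.

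**Longest gap from X-ray to the later test** = last day of the site-visit window − first day of the X-ray window:

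- Month 6: 190 − 170 = 20 days.
- Month 12: 370 − 350 = 20 days.
- Month 24: 750 − 690 = 60 days.

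The X-ray and site visit have the same nominal day, so the nominal gap is 0. These values are upper limits.

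**Age of the last scheduled test when the X-ray is taken** = X-ray day − day of the preceding test:

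- Month 6, after Week 1: nominal 180 − 7 = 173; range 170 − 13 = 157 to 190 − 1 = 189.
- Month 12, after Month 6: nominal 360 − 180 = 180; range 350 − 190 = 160 to 370 − 170 = 200.
- Month 24, after Month 18: nominal 720 − 540 = 180; range 690 − 550 = 140 to 750 − 530 = 220.

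These intervals follow from the six-monthly schedule, and the protocol sets no maximum age for a test. They show only that an earlier scheduled test cannot stand in for one taken just before the X-ray.

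**Column alignment in Table 2.** In the text copy reviewed, the test marks appear to sit under Screening, Week 1, X-ray Month 6, X-ray Month 12, Month 13 and Month 24. The row is probably shifted, because a Month 13 mark makes little sense when Month 18 needs one, and the GAIS row above it also looks displaced. There are two possibilities:

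- If the row is shifted, the Month 6 and 12 marks belong to the site visits. Table 2 then agrees with section 9.2 on the visit, and both conflict with footnote α.
- If the marks are literal, Table 2 puts the Month 6 and 12 tests at the X-ray visits and section 9.2 puts them at the site visits.

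The Month 24 mark is under the site visit as printed. Either way, section 9.2 needs correcting.

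**The case against.** The strongest counter-argument turns on the word *or* in footnote α. One footnote serves the whole row, so it could mean before whichever procedure follows at that visit. At Months 6 and 12, section 9.2 lists the test just ahead of the retreatment, and on that reading the rule is satisfied whenever retreatment is given. This softens the conflict for retreated subjects. It does not help subjects X-rayed at Month 6 or 12 who are not retreated, and retreatment is optional. Nor does it help at Month 24, where there is no treatment.

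Other points on that side are fair:

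- The 20- and 60-day gaps are extremes of identical windows. Visits on the same day would shorten the gap to almost nothing, although the order would still be wrong.
- Discontinuation for pregnancy has little force at Month 24, because participation ends at that visit. What remains there is an exposure that cannot be undone.
- The study has 20 subjects, pregnancy and lack of effective contraception are exclusions, the protocol describes the radiation as low, and two of the three affected X-rays are conditional.
- The alignment of Table 2 at Months 6 and 12 is uncertain.

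These points limit the practical size of the problem. They do not reconcile footnote α with section 9.2.

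**Conclusion.** The concern holds. As written, a site that follows section 9.2 cannot test before the Month 6, 12 or 24 X-ray, although Table 2 calls for a test before X-ray. The failure is unconditional for subjects X-rayed at Month 24 and for those X-rayed but not retreated at Month 6 or 12. For subjects retreated at Month 6 or 12, it depends on reading footnote α as covering the X-ray as well as the treatment.

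The Month 6 X-ray applies to every subject. How many women of child bearing potential would be affected at any of the three time points cannot be determined, because the documents do not give that number. It is likely to be small. The conclusion rests on the section 9.2 text and the wording of footnote α, and does not depend on the cell positions in Table 2. It merits correction as a safety and consistency point, with no consequence for the statistical analysis.

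**What to change.** In section 9.2 and Table 2, schedule the existing Month 6, 12 and 24 urine tests for subjects of child bearing potential before the corresponding X-ray, for example on the same day at the site or at the imaging center. If the original Table 2 already places the Month 6 and 12 marks under the X-ray columns, those two need no move in the table. Keep a test before any retreatment, and leave the test at the site visit when no Month 12 or 24 X-ray is due. Add the Screening test to the section 9.2 text so that it agrees with Table 2 for the baseline X-ray.

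The Month 1 X-ray has no test scheduled and falls about 3 weeks after the Week 1 test (30 − 7 = 23 days nominally). Adding one there is an optional clinical choice and is separate from this contradiction.

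The cost is a urine test at the imaging center or a short stop at the site before the film, plus a second test when retreatment falls on a later day. No endpoint, sample size or analysis is affected.
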